## **6.8 Data Management, Data Safety Monitoring Board (DSMB), and Trial Monitoring**

**Data Management:** All data will be collected on case report forms by the research coordinator. The Methods Centre at the Ottawa Hospital Research Institute will be used to provide database design and data analysis services. The Coordinating Centre will be responsible for all aspects of the trial including day-to-day management.

**DSMB:** This study will be monitored by an independent DSMB, consisting of an independent epidemiologist, and three physicians not involved in this study. The DSMB will be immediately informed of any serious adverse events (SAEs), which are potentially related to study drug.

The DSMB is responsible for assuring that study participants in AMPLCaRe are not exposed to any unnecessary or unreasonable risks and that the study is being conducted according to the highest scientific and ethical standards. In order to carry out this responsibility, the DSMB will:

- Familiarize themselves with the Terms of Reference, study protocols, manuals and any amendments that are developed as the study progresses.
- Review descriptive reports and interim analyses.
- Provide recommendations for or comments regarding change(s) to the design or methodology of the clinical trial.
- Provide feedback on ancillary studies.
- Alert investigators regarding emerging procedural or ethical issues.
- Comment on the relevancy of new external published data from other trials that may impact on patient safety or efficacy of the study treatments.

DSMB members will review data only by masked study group (such as A vs. B rather than experimental vs. control). The DSMB may request unblinded safety data tables, in cases of adverse events associated with study drug or procedures. Serious adverse events, which are of

## NSCLC Adjuvant melatonin RCT

concern to members of the Steering Committee (potentially study drug related) will also be reviewed by the DSMB.

If at any point the DSMB considers continuance of the study unacceptable, the sponsor will be immediately notified.

**Trial Monitoring:** Monitoring will be conducted by qualified research personnel according to the trial monitoring plan developed in conjunction with OHRI administration. Essential regulatory documents as laid out in section 8 of ICH/GCP will be reviewed in addition to performing risk based source document verification.

### **6.9 Adverse Events**

An “adverse event” means any adverse occurrence in the health of a clinical trial subject who is administered a natural health product, that may or may not be caused by the administration of the natural health product, and includes an adverse reaction, a serious adverse reaction and a serious unexpected adverse reaction.

According to the Health Canada approved product monograph, expected adverse events associated with melatonin include fatigue, nausea, vomiting, and cramping. Though rare, allergic reactions have been reported. Morning fatigue may occur with greater frequency at the beginning of the study [76]. Patients should be informed that melatonin should not be consumed with alcohol, other medications or natural health product with sedative properties.

In a review of scientific literature, in very rare cases (only 9 out of 307 articles reported adverse effects), the following reactions of Melatonin were reported:

- Four cases of seizures
- Two cases of skin eruptions (skin rash)
- One patient with autoimmune hepatitis (chronic disease of the liver)
- One case of confusion
- One case of optic neuropathy (disease of the eye)
- Four cases of fragmented sleep
- One psychotic episode
- One case of nystagmus (rapid involuntary rhythmic eye movement)
- One case of headache

Given the anecdotal nature of much of this evidence, however, it is debatable whether or not Melatonin was the true cause of the adverse events reported. The adverse effects of melatonin appear to rest on a limited number of studies and case reports. However, few studies have been conducted to establish the veracity of attributing these effects to melatonin.

Interaction of melatonin with nifedipine is perhaps the best documented interaction in that it has evidence from a randomized controlled trial, albeit a small one [77].

Patients taking nifedipine and concomitant melatonin showed a decrease in blood pressure control from baseline administration of nifedipine only. Therefore baseline and follow up

## NSCLC Adjuvant melatonin RCT

monitoring of blood pressure for patients taking nifedipine is warranted. This possible interaction will be flagged for all patients taking nifedipine with recommendations in the chart made to monitor for any unanticipated rise in blood pressure.

The incidence of all adverse events, expected and unexpected, and any steps taken to treat the complication will be documented in the patient's chart and study file and recorded on the Adverse Events case report form.. Adverse events should be communicated to the REB according to the REBs policies and procedures. The frequency and nature of serious adverse events will be documented and reported to the DSMB.

Adverse events will be tracked in the following situations:

- All patients on study up to the 2-year time point.
- Patients who started study capsules and withdrew within 2 years (will continue to follow radiographically, so AEs will also be tracked).
- Screen fails who started study capsules.

Adverse events will not be tracked in the following situations:

- Any patient beyond the 2-year follow up.
- Patients who recur within 2 years (will continue to be tracked for mortality only).
- Patients who did not start the study drug (screen fails or withdrawals).
- Prior to signing the consent form and starting the study intervention

Patients in this study may experience adverse events that would be considered expected for lung cancer patients. These events include the following:

- Pain
- Insomnia
- Fragmented sleep
- Lack of appetite
- Lung infection
- Pneumonia
- Shortness of breath
- Fatigue
- Depression/depressive symptoms
- Dizziness
- Cough

Furthermore, due to surgical complications, patients in this study may experience expected serious adverse events (considered serious by definition of prolonged hospitalization). These events include the following:

- Atelectasis
- Pneumonia
- Cardiogenic edema
- ARDS
- Empyema
- Effusion

## NSCLC Adjuvant melatonin RCT

- Hemothorax
- Prolonged air leak
- BP Fistula
- SubQ emphysema
- Atrial arrhythmia
- Ischemia
- Hypertension
- CHF
- Cardiac effusion
- UTI
- Renal insufficiency
- Non-infect. diarrhea
- Constipation
- Vomiting
- Ileus (bowel obstruction)
- Confusion
- Infection
- C-difficile
- Heart block

Patients in this study may also be undergoing chemotherapy or radiation treatment. As such it is reasonable to expect that they may experience adverse events related to this treatment, which include the following:

- Febrile neutropenia
- Nausea/vomiting
- Fatigue

It is possible that in some cases the events defined above may be related to the study drug (or exacerbated by the drug). The site investigator will assess the relationship of the study drug to the events listed above and the seriousness of the event (see 6.10 Serious Adverse Events)

Patients in this study could be diagnosed with a new primary cancer while on study. If this is the case, the new primary is reported as an adverse event. However, a recurrence of the lung cancer (outcome) will not be reported as an adverse event.

### **6.10 Serious Adverse Events (SAEs)**

According to the principles of ICH GCP, a serious adverse event is any untoward medical occurrence that at any dose: results in death, is life threatening, requires inpatient hospitalization or prolongation of existing hospitalization, results in persistent or significant disability/incapacity, or is a congenital anomaly/birth defect. When a serious adverse event is identified, the Serious Adverse Event form should be completed and signed by the lead principal investigator at the site. Please refer to the AMPLCaRe Procedures Manual, or contact the coordinating center should you have any questions or concerns.

The Natural Health Product regulations state that all **adverse events deemed to be serious and related/possibly related to the intervention are subject to expedited reporting to Health Canada**. These events are referred to as **Serious Adverse Drug Reactions (SADRs) and can be either expected (SADRs) or unexpected (SUADRs) in nature**. Therefore, if an event is determined to be **serious, and related/possibly related to the intervention, regardless of expectedness**, it must be reported to the coordinating center within 24hrs of becoming aware of the event and subsequently reported to the site REB according to their policies and procedures.

The coordinating center will notify Health Canada as soon as possible but no later than 7 calendar days after becoming aware of the event for fatal or life threatening events and no later than 15 days after becoming aware for non fatal/life threatening events. Please refer to the AMPLCaRe Procedures Manual, or contact the coordinating center should you have any questions or concerns.

### **6.11 Contraindications/Drug Interactions:**

Patients who are pregnant or breastfeeding are excluded from participation in this trial. Inclusion of participants with a significant health conditions such as asthma, cardiovascular disease, chronic kidney disease, depression, diabetes or hypoglycemia, hormonal disorder, immune system disease, liver disease, migraines, seizure disorders will be considered on a case by case basis by the site investigator and coordinating center. In order to monitor for possible drug interactions, patients who are taking anticoagulants, anticonvulsants, blood pressure medications, immunosuppressive medications, sedative, hypnotic or psychotropic medications, or steroids will be advised by the research staff to advise their treating physician if they experience any change in their pre-existing conditions.

### **6.12 Premature withdrawal**

Patients who withdraw prematurely from the study will be encouraged to return for a final visit. By adhering to an intention-to-treat model, patients who withdraw from taking the study drug prematurely will be asked if they would be willing to be followed radiographically (including possible recurrence or mortality) up to a maximum of five years past their date of enrollment. If the patient agrees, the Research Coordinator will document this in the patient's chart and will continue to record the results of the standard of care chest x-rays and CTs, and whether the patient had a recurrence or death. The patients will no longer be given questionnaires to complete if they withdraw.

Considering the standard procedures patients will be following for their regular care and that this trial does not require any additional frequency of visits, we do not anticipate this to be a major concern.

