## **6.5 Outcome Measures**

The primary outcome is a composite outcome including either cancer recurrence and/or mortality within two years following the commencement of the intervention. Recurrence will be determined by clinical examination by the patient's thoracic surgeon in addition to radiological evidence of loco-regional or systemic recurrence of lung cancer. While contrast enhanced chest CT scan at one and two years post resection is the preferred radiological assessment, the standard of care radiological assessments for each site is acceptable. For study purposes, only chest CT is requested at 1 and 2 years, but results of head and abdominal CTs will be recorded if applicable. As per standard of care, lateral and P/A chest radiographs will be assessed at 3 weeks and at 3, 6, 9, 12, 18 and 24 months following hospital discharge.

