## NSCLC Adjuvant melatonin RCT

months, 9 months, 1 year, 18 months and 2 years. Information regarding the results from chest x-rays or CT scans, chemotherapy and/or radiotherapy treatment, recurrence and past medical history/concomitant medications will be captured from the patient's chart. All other information will be captured by the research coordinator through telephone conversations and follow up visits with the patients.

The research coordinator will make a follow up phone call once per week for the first two weeks and then as needed for the one year while the patient is on the study drug. During telephone conversations, the research coordinator will assess study compliance and any adverse or serious adverse events. Information regarding these phone calls will be captured in the patient's study records.

At follow up appointments, the research coordinator will provide the patient with study drug refills (up to the 1-year mark), provide quality of life questionnaires, monitor any adverse or serious adverse events and monitor compliance. Compliance will be monitored during a brief interview, and by checking for left over pills. Patient self-report is an acceptable measure of compliance if counting pills is not feasible. Patients will be asked at each follow-up phone call and visit if they have missed any capsules. Patient reports of start and end dates of the capsules will also be used to determine compliance.

The study will be extended to include follow up periods past the initial follow up period of two years. Specifically, patient follow up times will be extended to include follow ups with all patients enrolled on study beginning in 2007. Patients' records will be tracked to determine whether they experienced a recurrence or death. Participants will be followed until they either reach the five year maximum or until 2 years after the last participant was enrolled in the study. As such, each patient will have a varying follow up period (with a range of 2-5 years).

Extension of follow ups past the two year time point will be conducted as follows:

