Patients' medical records will be reviewed in order to record cancer recurrence or death. Should the information not be available in the medical records, their records will be requested from the Canadian Cancer Registry. If patient information cannot be found in the registry, surgeons will be asked to follow up with the patient's GP in order to find out whether they had a recurrence or died. If the patient's GP does not have this information, but directs us elsewhere, or if the medical records indicate that the patient was discharged to another facility (eg: another hospital), this facility will be contacted. At the facility's request, the signed patient consent form will be provided in order for them to release the information on the patient's death or recurrence. If this information cannot be retrieved through searching patient records in any of the above methods, patients will be contacted directly. Patient contact will begin with a letter and brief questionnaire to the last known address (letter and questionnaire provided by the coordinating centre) requesting an update on patient health status. If the patient does not respond to the letter, the study coordinator will contact the patient at their last known telephone number, and ask for a health status update. If the patient cannot be contacted, and all other options are exhausted, the study coordinator will contact the patient's next of kin (telephone script provided by the coordinating centre). Should we be unable to follow up in any of the above methods, participants

will then be considered lost to follow up. Sites should ensure that the letter, questionnaire, and telephone script receive REB approval prior to use.

Patients who 1) withdrew from the trial before starting the intervention, or 2) were enrolled but considered to be screen fails (did not meet inclusion criteria) and did not start the intervention, or 3) recurred within the first two years, will be followed only for outcome data (recurrence and/or mortality). The “Follow-up for Withdrawals and Screen Fails (who did not start intervention)” CRF will be completed annually for these patients (up to 5 years post-op). Adverse events will not be tracked for these patients.

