## 8. Statistical Analysis

The primary analysis will be performed using an ‘intention to treat’ analysis. Using this approach, patients will be included in the analysis according to the group to which they were randomized regardless of cross-over or compliance. Baseline characteristics of patients in the two treatment arms will be assessed using frequency distributions and univariate descriptive statistics including measures of central tendency and dispersion. As a complementary approach,

we will also conduct a treatment received as ‘per protocol’ analysis of the primary outcome measures. Baseline characteristics in the two treatment arms will be compared using univariate descriptive statistics.

The primary analysis of the composite outcome of two-year cancer recurrence and mortality will be conducted using an unadjusted chi-square test comparing the proportion of events in each of the two treatment groups. This will be translated into a relative risk (RR), relative risk reduction (RRR), absolute relative risk (ARR), and number needed to treat (NNT). In addition, a logistic regression procedure will be employed to adjust exacerbation proportions using covariates that are either clinically important prognostic risk factors or unbalanced at baseline.

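### Follow-up rules for patients who start capsules and then stop conflict across Sections 6.6, 6.9 and 6.12, so two-year primary-endpoint status may be missing in those who decline further follow-up

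*Combined protocol and SAP*

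**What the plan says.** The primary outcome (Section 6.5) is "cancer recurrence and/or mortality within two years following the commencement of the intervention". Section 8 analyses it by intention to treat, so that "patients will be included in the analysis according to the group to which they were randomized regardless of cross-over or compliance", with an "unadjusted chi-square test comparing the proportion of events in each of the two treatment groups". Section 8 gives no rule for a missing two-year outcome.

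Three sections deal with patients who leave treatment:

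- Section 6.12: "patients who withdraw from taking the study drug prematurely will be asked if they would be willing to be followed radiographically", up to five years from enrolment. The coordinator goes on recording imaging, recurrence and death on condition that the patient agrees. What happens after a refusal is not stated.
- Section 6.9, among those whose adverse events are tracked: "Patients who started study capsules and withdrew within 2 years (will continue to follow radiographically, so AEs will also be tracked". No condition is attached.
- Section 6.6: an annual outcome-only form for patients who "withdrew from the trial before starting the intervention", for screen failures who never started, and for patients who recurred in the first two years. Patients who start and then stop are not on this list.

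Section 6.6 also sets out tracing steps: medical records, cancer registry, family doctor, other facility, letter, telephone, next of kin. They are introduced by "Extension of follow ups past the two year time point will be conducted as follows".

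**The concern.** An intention-to-treat comparison of two-year proportions needs a two-year status for every randomised patient. The test has no censoring to absorb unknown outcomes. Section 6.12 invokes the intention-to-treat model, yet it adds an agreement step that can leave a randomised patient without an outcome. The steps that would recover a missing status are written for a later period.

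If those who stop and decline differ from the rest in prognosis, and the two arms differ in how many or which patients decline, the patients left in the analysis are no longer a randomised comparison. Such a difference is plausible but not shown: Section 6.9 lists fatigue, nausea, vomiting and cramping as expected with melatonin. Even loss that is balanced and uninformative costs power.

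**Working it through.** **1. The rules side by side**

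- *Started, then stopped:* 6.12 follows on agreement and is silent on refusal; 6.9 follows without condition; the 6.6 outcome-only list does not mention them.
- *Never started:* 6.6 follows annually for recurrence and death, up to five years after surgery, and does not mention agreement.
- *Status unknown by year two:* 6.6 takes imaging and recurrence data from the chart, but gives no tracing steps for this time point.
- *Status unknown after year two:* 6.6 gives the full set of steps.

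**2. Could the extension recover two-year status?**

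In part. It covers all patients enrolled since 2007, and Section 4 collects dates of recurrence and death, so a later trace that finds a date also settles the two-year status. There are two limits. The agreement sought in 6.12 runs to five years, so on its wording a refusal also reaches the extension. And follow-up ends at five years or two years after the last enrolment (6.6; Section 10 closes the study then), so the last-enrolled patients have little or no time beyond year two.

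**3. The plan's own power figure**

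Inputs from Section 7: 320 per arm, 5% reference rate, differences of 6 and 7 points, stated power 80% and 90%. Two-sided alpha of 0.05 is assumed, since none is stated.

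Power = Φ{[d − 1.96·√(2p̄(1−p̄)/n)] / √([p1(1−p1)+p2(1−p2)]/n)}

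- 5% v 11%: (0.06 − 0.0420)/0.0213 = 0.84, power 80.0%
- 5% v 12%: (0.07 − 0.0432)/0.0219 = 1.22, power 89.0%

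The stated figures reproduce with all 320 per arm evaluable, so they allow for no missing outcomes. Under assumed loss:

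| Loss | n per arm | 5% v 11% | 5% v 12% |
|---|---|---|---|
| 5% | 304 | 78.0% | 87.4% |
| 10% | 288 | 75.7% | 85.6% |
| 15% | 272 | 73.3% | 83.5% |
| 20% | 256 | 70.7% | 81.2% |

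**4. Possible bias with no true effect**

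Overall rate p = 20% in both arms (a rate that Section 7 considers possible). The fraction missing, d, and the event rate among the missing, e, are assumptions. Observed rate = (p − d·e)/(1 − d).

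- d = 10% melatonin, 5% placebo, e = 40% in both: (0.20 − 0.04)/0.90 = 17.8%; (0.20 − 0.02)/0.95 = 18.9%. Unrounded, 17.78% v 18.95%, a false difference of 1.2 points.
- The same patients counted as event-free: 0.20 − 0.04 = 16.0%; 0.20 − 0.02 = 18.0%; 2.0 points.
- d = 10% in both, e = 40% v 20%: 17.8% v 20.0%; 2.2 points. With d = 5% in both: 18.9% v 20.0%; 1.1 points.
- d and e equal in both arms: no false difference.

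For scale, the standard error of the difference is √(2×0.20×0.80/320) = 3.2 points. A shift of 1.17 points is 0.37 of that and raises a nominal 5% two-sided error to about 6.6% (0.056 + 0.010, from P(Z > 1.59) and P(Z < −2.33)).

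Extreme bound: if 16 of 320 per arm (5%) are unknown, the choice between all events and no events spans 5 points in each arm's rate.

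**The case against.** A reader might infer that the two-year endpoint is lost in everyone who stops and declines. The documents do not go that far. Section 6.12 is silent on decliners, 6.9 states continued follow-up, 6.6 takes much of the outcome from the chart, and a later trace could recover a date. This part of the objection stands: the supportable word is *may*. It does not remove the problem, for the two reasons in step 2 of the working.

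A reader might also infer that no agreement is needed, because 6.6 says that "the signed patient consent form will be provided in order for them to release the information" on recurrence or death. That shows how the form is used at another facility's request. It does not show that permission survives a patient's withdrawal, and the consent text is not available to check.

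Nor can it be said that patients exposed to the drug have the weakest rule. Section 6.9 gives those who started more follow-up (imaging and adverse events) than 6.6 gives non-starters, and the silence of 6.6 on agreement is not proof that none is sought.

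Section 6.12 also partly draws the needed distinction, since it refers separately to leaving the study and to stopping the drug. It notes that the trial adds no visits to regular care, so refusals may be few. Finally, arm-dependent stopping is uncertain: fatigue is expected in these patients anyway, and the trial's own hypothesis is less fatigue on melatonin. These points limit the likely size. They do not settle which of the conflicting rules applies.

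**Conclusion.** The point holds as an inconsistency with a possible effect on the primary endpoint. On its wording, 6.12 can leave randomised patients who stop and decline without a two-year status; 6.9 says otherwise; 6.6 does not list these patients; and no tracing steps are assigned to the two-year time point.

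The size is unknown, because the documents give no rate of stopping or of refusal. If nobody declines, nothing changes. Under the assumed rates the false difference is about 1 to 2 points, well under one standard error, and 10% loss costs about 3 to 4 points of power. The extreme bound for 5% missing is as wide as the 20% to 15% difference in Section 7, but it is a bound and not an expected bias. This is a cheap improvement worth making, not evidence that the primary analysis fails.

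**What to change.** Reconcile Sections 6.6, 6.9 and 6.12 into one rule that separates stopping capsules from withdrawing consent for data:

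- By default, patients who stop capsules stay in records-based follow-up for recurrence, death and standard-of-care imaging, as far as the signed consent allows, unless they explicitly withdraw consent for use of their records. Check the consent form on this point and amend its wording if needed.
- Add patients who start and then stop to the outcome-only form in 6.6.
- Apply the existing tracing steps to any patient whose two-year status is unknown, not only to follow-up past two years.
- Record on the case report form which of the two happened: stopped capsules, or withdrew consent for data.

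The cost is protocol wording, one case-report-form item, a consent-wording check at each ethics board and slightly more chart review. Patients who do withdraw consent for their records will still have an unknown outcome. The follow-up rule cannot settle how they count, and Section 8 would still need to say so.
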